We propose a phase IIa study to determine the optimal dose of vitamin E and its mechanism and site of action. In this study we aim to enroll up to 90 patients with NAFLD. Initially, all patients will undergo 12 weeks of intensive lifestyle modification. Following that, all patients will be randomized to treatment with 3 different doses of natural vitamin E (rrr- α -tocopherol at 200, 400 or 800 IU/d) for 24 weeks. The primary end points for efficacy are normalization of liver enzymes and reduction in liver fat contents by magnetic resonance spectroscopy. Patients will undergo liver and adipose tissue biopsies before vitamin E treatment and after 4 weeks of therapy, and the biopsy samples will be used to measure changes in gene expression and markers of oxidative stress. This will be coupled with extensive phenotyping before and after treatment using serological, radiological and dynamic endocrine testing and is aimed at finding the dose-response characteristics of vitamin E in NAFLD, and allowing us to understand the mechanism of its action.

After 24 weeks of randomized treatment, all patients will be switched to a dose of 800 IU/ml and will continue treatment for up to 30 months, at the end of which another liver biopsy will be performed. From this phase we will assess the effects of dose increase of vitamin E on liver enzymes and fat content, and will determine the effect of long-term treatment on histological outcome.

Table of Contents

Précis	3
Table of Contents	4
Introduction	6
Non-alcoholic fatty liver disease	6
Vitamin E	7
Vitamin E for NAFLD	8
Aims	10
Primary Aims:	10
Secondary aims:	10
Study design and methods	11
Overall design (Figure 3)	11
Initial screening and enrollment	12
Run-in phase and lifestyle intervention	12
Detailed in-patient assessment	14
Vitamin E Treatment	15
Extended Treatment Phase	16
Details of procedures	18
Adipose Tissue Biopsy	18
Liver Biopsy	18
Magnetic Resonance Spectroscopy	19
Justification for study design	19
Run-in phase	19
Liver biopsies	20
Absence of a control arm	21
Duration of treatment	21
Inclusion and exclusion criteria	21
Inclusion	21
Exclusion criteria	
Monitoring subjects and criteria for withdrawal of subject from the study	
Analysis of the study	
End points	27

Vitamin E for Non-Alcoholic Fatty Liver

Primary end points	27
Secondary end points	27
Basic scientific end points	27
Statistical analyses	28
Sample size calculation	28
Human subject protections	28
Rationale for subject selection	28
Recruitment strategy	29
Informed consent process	29
Evaluation of benefits and risks	30
Benefits	30
Risks and Discomforts	30
Adverse event reporting and data monitoring	33
Monitoring	34
Collection and storage of human specimens or data	35
Remuneration/compensation	35
References	38

Introduction

Non-alcoholic fatty liver disease

Non-alcoholic fatty liver disease (NAFLD) is the most common cause for liver enzyme abnormalities in the western world. This disorder, consisting of abnormal accumulation of triglycerides in the liver, is estimated to affect approximately 30% of the US population¹. NAFLD commonly exists with features of the metabolic syndrome (obesity, hypertension, diabetes mellitus and hypertriglyceridemia) and its rising prevalence seems to accompany the increasing rates of obesity.

A subset of patients with NAFLD develop non-alcoholic steatohepatitis (NASH), where the fat accumulation is accompanied by hepatocellular injury, inflammation and fibrosis. NASH can be a progressive disease, leading to cirrhosis, liver failure and hepatocellular carcinoma. NASH and NAFLD are also associated with increased cardiovascular mortality, even in patients without other "classical" cardiovascular risk factors.

The pathogenesis underlying NAFLD and NASH is not clearly understood. Insulin resistance is commonly, but not universally, seen in these patients but it is unclear whether it is causing the fat accumulation or is being caused by it. Triglyceride storage in the liver may have a physiological role as a protective mechanism in the face of increased free fatty acid (FFA) flow from adipose tissue. When the ability of the hepatocytes to store these fatty acids as non-toxic triglycerides is overwhelmed, hepatic lipotoxicity ensues, while peripheral lipotoxicity worsens muscle insulin resistance and pancreatic beta-cell function². The accumulation of free fatty acids in hepatocytes causes endoplasmic reticulum (ER) stress, an increase in reactive oxygen species (ROS) and apoptosis. This is accompanied by inflammatory cell infiltration, an increase in inflammatory cytokines³, activation of macrophages and stellate cells and fibrosis.

Innate immune cells such as natural killer T (NKT) cells and natural killer (NK) cells are thought to contribute to the disease pathogenesis. NKT cells, for example, get activated by lipids and, in a TIM-1-mediated fashion, by apoptotic hepatocytes⁴, produce cytokines that promote fibrosis and then undergo apoptosis themselves. CD1d-deficient mice that lack NKT cells are protected from fibrosis⁵. NK cells are activated by cytokines and by altered surface marker expression by hepatocytes, and are able to exert rapid effector functions such as cytokine production and cytotoxicity. Both NKT and NK cells constitute the major lymphocyte population in the liver.

There is a marked heterogeneity in the presentation and phenotype of patients with NAFLD. Racial and ethnic variability is significant; for example, Asian patients tend to have NAFLD at lower BMIs than their Caucasian counterparts, African-Americans seem to be relatively protected and Hispanics are at increased risk. Genetic factors clearly play a role, with most data pointing towards variants in the PNPLA3 (adiopnutrin) gene as strongly associated with disease occurrence and severity⁶. However, it is still unclear why some patients develop NASH and progressive disease, while others remain in the relatively benign steatotic stage. To date, no test apart from a liver biopsy accurately differentiates NASH from steatosis.

Currently, there is no standard approved therapy for NASH. Life style modification is routinely advocated, although only recently it was actually shown to benefit patients⁷. Diet, weight loss and physical exercise improve insulin sensitivity not only at the hepatic level, and thus have an important role in reducing the release of FFA from adipose tissue⁸. For patients who are not able to gain benefit from lifestyle changes, a logical choice is pharmacological intervention.

Vitamin E

Vitamin E is a fat-soluble antioxidant that is believed to be important in maintaining the integrity of lipid membranes and preventing oxidative injury to lipids, cholesterol and cell signaling molecules. Clinically apparent vitamin E deficiency is rare and is usually associated with severe malabsorption syndromes, advanced liver disease or inherited deficiencies in vitamin E transport proteins. In adults, vitamin E deficiency is associated with neuropathy and ataxia. In animals, vitamin E deficiency is associated with reproductive failure and with poor fetal neurological development.

The term "Vitamin E" is a collective name for several fat-soluble compounds; naturally occurring vitamin E exists in multiple chemical forms (α , β , γ , and δ -tocopherol and – tocotrienol), which have variable levels of antioxidant activity and biologic effects in different cell systems. In humans, however, only α -tocopherol appears to have significant biologic effects. There are 3 chiral centers in the α -tocopherol molecule, yielding 8 possible racemic isomers; of these, RRR- α -tocopherol is the most active form and the one that is present in nature, while isomers with S chirality in the first chiral center are inactive and are not accumulated in tissues.

Vitamin E is present naturally in many foods and is absorbed in the intestine only in the presence of fats. The recommended daily intake for adults is 15 mg (22.4 IU) of d-alphatocopherol. Even this low amount is actually more than the average American consumes daily; in fact, it is estimated that about 90% of Americans are marginally deficient in vitamin E intake from dietary sources 10 . Multiple vitamin E supplements are available and an estimated 11% of the adult US population takes vitamin E supplement daily (which usually have 400 IU). Vitamin E is also present in many multivitamins, but usually in lower amounts (40-50 IU). Vitamin E supplements are manufactured from different sources and by different techniques. Synthetic supplements are the least expensive and contain and all-racemic mixture of all isomers, and thus have a potency of $\sim\!50\%$ that of natural vitamin E, which contains mostly or purely RRR- α -tocopherol. Both formulations are available over the counter.

The absorption of vitamin E is dependent upon the presence of dietary fat. Thus, even if vitamin E supplements are taken, if not taken with a meal that has at least some fat, absorption will be minimal. Vitamin E from the intestines is taken up into chylomicrons, transported to the circulation via the thoracic duct and then rapidly and almost completely extracted from the post-prandial blood by the liver. In the liver, rrr- α -tocopherol is bound by the tocopherol transfer protein (TTP), which can deliver it into and across lipid membranes. The other forms of vitamin E (l- α -tocopherol and γ -tocopherol) for instance) are not bound to TTP and are metabolized by the liver and excreted in bile. Thus, the specificity of TTP for rrr- α -tocopherol is what determines that this form of vitamin E is the

biologically active form in humans. The hepatic TTP also allows for vitamin E to be secreted into the blood where it is taken up by HDL and LDL lipoprotein particles. These lipoprotein particles deliver vitamin E to other tissues. Inside of cells, vitamin E remains bound to lipids and can act to protect intracellular membranes from free radical damage probably by forming transient oxidative intermediates and delivering the free electrons to other anti-oxidants such as vitamin C¹¹. The overall effects of vitamin E are multiple, perhaps because it protects membrane bound enzymatic and cell-signaling molecules non-specifically which are involved in a multitude of activities. Vitamin E also appears to have its major effect in the presence of environmental oxidative stress, so that cells are more able to resist injury when vitamin E replete.

The antioxidant activities of vitamin E and epidemiologic evidence linking vitamin E intake to several diseases led to extensive, large scale studies of vitamin E for prevention of cancer as well as cardiovascular and cerebrovascular disease. While controversial, overall these studies showed little or no effect of vitamin E supplementation on subsequent cancer or cardiovascular events. Indeed, perhaps the most reproducible effect seen was a slight increase in hemorrhagic stroke¹² that has been attributed to the anti-platelet effects of higher doses of vitamin E. For these reasons, vitamin E supplementation has become more controversial.

Vitamin E for NAFLD

The anti-oxidant effect of vitamin E can potentially ameliorate the lipotoxicity and ROS-induced damage in NASH and affect disease progression. Several treatment trials were conducted with inconclusive results seen in the smaller studies¹³. However, two recent studies have suggested that vitamin E may be beneficial in nonalcoholic fatty liver disease (NAFLD) and nonalcoholic steatohepatitis (NASH) and that a surrogate marker for its effect might be serum alanine aminotransferase (ALT) levels.

The PIVENS trial¹⁴ was a double-blind, double-dummy placebo-controlled trial conducted at 8 U.S. medical centers in 286 adults with liver biopsy proven NASH who took either pioglitazone (30 mg), vitamin E (800 IU of rrr-α-tocopherol) or placebo daily for 2 years (96 weeks) with regular monitoring of serum enzymes and liver biopsy done before and at the end of treatment. Follow up also occurred 24 weeks after stopping the interventions. The primary endpoint was improvement in liver histology which was statistically significant comparing placebo to vitamin E with decreases in steatosis, inflammation and cell injury scores, but little change in fibrosis (Figure 1, Panel A). In addition, there were marked differences in ALT levels during treatment and this effect was seen within 6 months of starting therapy (Figure 2, Panel A). Overall, histological and biochemical response were achieved in 43% of patients treated with vitamin E in this study.

The TONIC trial 15 was a similar double-blind, double-dummy placebo-controlled trial conducted at the same 8 U.S. medical centers in 116 children or adolescents with biopsy-proven NAFLD who took either metformin (1000 mg), vitamin E (800 IU of rrr- α -tocopherol) or placebo daily for 2 years (96 weeks) with regular monitoring of serum enzymes and liver biopsy done before and at the end of treatment. The primary endpoint was improvement in ALT, even though liver histology was also obtained, largely because liver histologic changes had never been documented in children before this study. There

were statistically significant differences in ALT levels between vitamin E and placebo treated children at 6 months and one year, but the differences were no longer significant at 2 years largely because of improvements in the placebo group (Figure 2, panel B). Importantly, there were improvements in liver histology in steatosis, inflammation and cell injury, although they were significant only for cell injury (Figure 1, panel B).

[figure not shown]

Figure 1 – Histological changes in vitamin E studies

[figure not shown]

Figure 2 – Changes in serum ALT in vitamin E studies

While these two studies showed convincing evidence that vitamin E has an effect on NAFLD and NASH, they also raised many issues regarding optimal treatment and

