Randomization will be done by the Clinical Center pharmacy Protocol Support Service and will be stratified by the result of the liver biopsy (classified as definite steatohepatitis, steatosis without steatohepatitis, or borderline^{21, 22}) and by the presence or absence of diabetes mellitus type 2 at enrollment. Patients will be monitored on weeks 1, 2, 3, 4, 8, 12, 16, and 20 of treatment. On each visit, fasting blood tests for Chem-20, insulin, C-peptide, free fatty acids and vitamin E levels will be drawn, vital signs including weight will be measured and a symptom questionnaire will be administered. CBC, lipid panel, apolipoproteins and urinalysis will be drawn every 4 weeks. A nurse will determine weight, vital signs and symptoms on every visit. A physician will evaluate the patients every 4 weeks. A serum sample for research purposes will be drawn on each visit and stored in -80°C.

On week 4 of treatment, patients will be admitted for a second liver biopsy and adipose tissue biopsy, and will have a repeat of the MR spectroscopy and FSIVGTT.

On week 24 of treatment, all patients will be admitted for an exit work-up, identical to the detailed in-patient assessment described above, but without the biopsies.

During the treatment, patients will be recording medication intake on a diary that will be collected every visit and will be used to assess compliance.

Extended Treatment Phase

On discharge, all patients will be offered to continue treatment with open-label vitamin E 800 IU/d (two 400 IU capsules taken once daily) for up to 120 more weeks, after which, an exit liver biopsy will be performed. Enrollment into the extended treatment phase is optional and refusal will not exclude the patient from the study. The medication intake diary will be used in this phase as well.

After 24 weeks in the extended phase (week 48 of the study), patients will undergo an additional MR spectroscopy. Based on the results of the MRS and liver enzymes, the response will be assessed prior to deciding on treatment continuation. For this purpose, response is defined as a decline of >=25% in ALT or normal ALT or normal AST or an absolute decline of more than 2% in liver fat content by MRS. The response criteria are selected to be sensitive, but not necessarily specific, aiming to predominantly identify patients who are not responding to treatment and in which continuation is futile. Based on the response assessment there are three possible outcomes (Figure 4):

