The second biopsy will be performed 4 weeks after starting vitamin E. The goal of this procedure is to obtain tissue to observe the effect of vitamin E on hepatic and adipose tissue gene expression. The histological response to pharmacological agents is slow and we do not anticipate a marked decrease in liver fat during these 4 weeks. This biopsy will allow us to detect an effect of vitamin E on gene expression and fatty acid metabolism without being confounded by the effects on the transcriptome of the decrease in liver fat. This biopsy is a purely research procedure and is not anticipated to provide clinical benefit; this will be clarified to the patients on enrollment, and again before the procedure.

A third liver biopsy will be performed in patients who agree to continue with extended vitamin E therapy, after 3 years of treatment. This biopsy will allow determination of histological response, especially whether the beneficial effects of vitamin E extend to halting progression of fibrosis. Although repeating liver biopsies in patients with NAFLD is not standard clinical practice, this biopsy is anticipated to provide important clinical information regarding the individual patient response and restaging, as well as research data.

At the liver diseases branch, we have acquired considerable experience in the performance of liver biopsies for clinical and research indications. Several LDB past and present studies, as well as studies in other institutions in viral hepatitis and in fatty liver diseases employed more than one biopsy, with good patient acceptance, safety track and important data acquired.

Absence of a control arm

A placebo-controlled arm could be considered in this study. However, by including a fourth arm we would markedly reduce our sample size in each arm and the statistical power to detect differences. Furthermore, we do not think it would be justified to perform a second

liver biopsy on patients treated with placebo. The lead-in phase should eliminate most of the placebo effect, and the use of paired biopsies for the analysis will allow us to control for inter-individual changes.

Duration of treatment

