After the run-in phase, patients will be admitted for up to 5 days, for the initial biopsies and extended tests as detailed above. At the LDB, it is our standard practice to keep all patients for observation overnight after a biopsy, and to perform a routine complete blood count 6 hours after the procedure. Following discharge, patients will be seen in the

outpatient clinic for the first 3 weeks of treatment, and will be subsequently admitted during the 4th week of treatment, for the second biopsy. At this stage, visits that are within 2 days before or after the scheduled visit date will not be considered a protocol violation. Following the second admission, the patients will be followed in clinic every 4 weeks. From this time point onwards, visits that are within 1 week before or after the planned visit date will not be considered a protocol violation. Patients will be admitted again at the end of the 24 week period for another extensive evaluation. During the extended treatment phase, patients will be seen every 12 weeks.

Patients will also be monitored as appropriate for patients with liver disease. Specifically, patients with liver cirrhosis or high-risk for hepatocellular carcinoma (HCC) will undergo surveillance for HCC by ultrasound or cross sectional imaging every 6-12 months, or according to most current guidelines. Patients with cirrhosis will be monitored by endoscopy as appropriate for the development of esophageal varices.

Patients who become pregnant during the study will be withdrawn, as pregnancy and associated hormonal and metabolic changes may affect hepatic fat metabolism and will confound the analysis. Patients who do not respond to treatment by week 48 will be withdrawn for futility. There are no other pre-specified criteria for withdrawal of patients from the study. Patients will be withdrawn if, according to the best judgment of the treating physician or the principal investigator, continuing treatment poses an unacceptable risk to the patient.

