Gene expression in liver and adipose tissue will be analyzed using microarray and quantitative PCR (qPCR) of tissue samples. Treatment-induced changes or comparisons between groups of patient (i.e. comparison of baseline expression between responders and non-responders) will be expressed as fold-induction.

NK and NKT cell changes in the serum and liver tissue will be analyzed using phenotyping and functional assays.

Oxidative stress will be measured in the serum, urine, liver and adipose tissue using TBARS assay, F₂-isoprostanes, 9-HODE, 13-HODE, SOD activity or similar measures. In women of child-bearing age, the phase of the menstrual cycle will be recorded on extended visits, as F₂-isoprostane levels can be affected by it.

Statistical analyses

Parameters of response to treatment will be analyzed by matched-pair comparison between pre-treatment and end of treatment values. Student's t-test will be used for values that are distributed normally while Wilcoxon's sign-ranked test will be used for non-parametric values. Categorical comparisons will be performed using X^2 or Fisher's exact test, as appropriate. The Cochran-Armitage test for trend will be used to test for a dose effect on the primary clinical end points.

To determine the effect of genetic variants, genotype-based analyses will be preferred to allelic analyses, with an additive model used primarily, unless other (dominant or recessive) models seem more appropriate. Linear or ordinal logistic regression will be used.

All analyses will be done with and without stratification for the presence of diabetes mellitus.

An $\alpha \le 0.05$ will be used to determine statistical significance.

Sample size calculation

The main goal of the study is to understand and characterize the mechanism of response to vitamin E. An important goal of the study is to simultaneously collect liver and adipose tissue to determine the site of action of the vitamin E and the relative contribution of each tissue to the disease. For most of the planned end points, including changes in liver fat content by ¹H-MRS and the basic scientific end points, there is not enough pre-existing data to allow for accurate sample size calculation.

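### Exit biopsies come only from patients who opt into the extension and pass the week-48 response rule, so a before-after comparison can be expected to overstate the long-term histological effect.

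*Combined protocol and SAP*

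**What the plan says.** The précis states that after the 24 randomized weeks "all patients will be switched to a dose of 800 IU/ml and will continue treatment for up to 30 months", that another liver biopsy follows, and that this phase "will determine the effect of long-term treatment on histological outcome". Under Justification for study design, Liver biopsies, the third biopsy is meant to show histological response, "especially whether the beneficial effects of vitamin E extend to halting progression of fibrosis".

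The body of the protocol narrows who gets that far:

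- Extended Treatment Phase: "Enrollment into the extended treatment phase is optional and refusal will not exclude the patient from the study".
- The same section, with Figure 4: at week 48, patients meeting none of the response criteria relative to baseline stop treatment. Any one criterion is enough to pass: an ALT fall of at least 25%, normal ALT, normal AST, or an absolute fall in liver fat of about 2 points. The section says the criteria were chosen for sensitivity rather than specificity.
- Monitoring subjects and criteria for withdrawal: "Patients who do not respond to treatment by week 48 will be withdrawn for futility". Patients with hemoglobin below 10 g/dL also skip the third biopsy.
- Liver biopsies: "A third liver biopsy will be performed in patients who agree to continue with extended vitamin E therapy, after 3 years of treatment". Table 1 places it at week 144 and schedules none at futility withdrawal.

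The Liver biopsies section names the baseline biopsy as the comparator for the exit biopsy. Under Statistical analyses, "Parameters of response to treatment will be analyzed by matched-pair comparison between pre-treatment and end of treatment values". That section gives no population for the exit biopsy and no rule for patients without one. A placebo arm was considered and rejected (Absence of a control arm).

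**The concern.** The question posed is what long-term vitamin E does to histology in the patients treated. The data that will answer it come from patients already selected on their response to treatment. The protocol itself links enzymes to histology: the Primary end points section chose its biochemical cut-offs because, in the sponsor's pilot, they were the rule most strongly associated with histological response. If week-48 response and histological change are positively related, removing week-48 non-responders removes, on average, the less favourable biopsies. The paired mean then looks better than it would in everyone who started, even with no long-term effect.

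The run-in and the pairing of biopsies, which the protocol offers in place of a control arm, do not correct this, because the selection happens after baseline. Without a comparator, stable fibrosis in the remaining patients cannot be read as treatment having stopped progression. At stake are the one long-term claim in the précis and the research rationale for a third invasive biopsy.

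**Working it through.** **Figures in the plan.** The documents give no figure for the exit biopsy. The only sample-size calculation (25 per group, 80% power, Cochran-Armitage test) concerns the 24-week biochemical end point. It reproduces (exact two-sided power 0.797 with equally spaced scores) but does not bear on this point.

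**Assumed inputs, none of them in the documents.** Share passing week 48, f = 0.75, 0.90 or 0.95. Correlation r between an underlying week-48 response index and histological change = 0.3 to 0.5. Exit biopsies n = 30 to 45. True mean change zero. Opting in is taken as unrelated to outcome.

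**Shift in the mean.** For a normal index cut at c so that a fraction f passes, the mean histological change among those passing moves by r × φ(c)/f, in SD units, where φ is the standard normal density.

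- f = 0.75: c = −0.674, φ(c) = 0.318, φ(c)/f = 0.424. Shift 0.3 × 0.424 = 0.13 to 0.5 × 0.424 = 0.21 SD.
- f = 0.90: c = −1.282, φ(c) = 0.1755, φ(c)/f = 0.195. Shift 0.06 to 0.10 SD.
- f = 0.95: c = −1.645, φ(c) = 0.103, φ(c)/f = 0.109. Shift 0.03 to 0.05 SD.

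**Chance of a false improvement.** Two-sided 5% paired t-test, upper tail only (nominal 2.5%), noncentral t with noncentrality √n × shift/SD, where the SD allows for the small reduction caused by truncation:

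| Pass rate | r = 0.3, n = 30 to 45 | r = 0.5, n = 30 to 45 |
|---|---|---|
| 75% | 10% to 13% | 22% to 32% |
| 90% | 5% to 6% | 8% to 10% |
| 95% | 4% | 5% to 6% |

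More biopsies raise these rates. With 75 patients entering (25 × 3) and 90% passing, about 68 are biopsied and simulation gives 7% (r = 0.3) to 12.5% (r = 0.5). At r = 0 the rate stays at 2.5%.

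**The same effect as a response rate.** Let h be the true proportion improved if everyone were biopsied, and let s and g be the shares passing week 48 among the truly improved and not improved. The rate among those biopsied is h·s/(h·s + (1 − h)·g). With h = 30% (assumed):

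- s = 1, g = 0.90: 0.300/0.930 = 32.3%.
- s = 0.95, g = 0.70: 0.285/0.775 = 36.8%.
- s = g = 0.70 (rule unrelated to histology): 0.210/0.700 = 30.0%, no bias.

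With all extension starters in the denominator and withdrawals counted as not improved, the rate is h·s: 30.0%, 28.5% and 21.0% in the three cases. That corrects the upward bias when the rule tracks histology, and understates benefit when it does not.

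**The case against.** **The rule is lenient.** A normal AST alone passes. Imaging plus metabolic syndrome is enough for entry, so some patients may have normal enzymes throughout; the Primary end points section expects some to be normal when vitamin E starts. A pass rate of 90% or more is plausible, and the bias is then small. This stands, and is why the range runs to 95%.

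**The correlation is assumed.** The pilot evidence concerns a different rule (AST ≤32 or ALT ≤35 U/L at end of treatment), not a week-48 screen applied about two years before the exit biopsy. For fibrosis the support is weak: the Introduction reports marked ALT differences in the adult trial but little change in fibrosis. This also stands.

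**Histology is not a listed end point, and the matched-pair sentence is generic.** True, and it limits the severity. But the précis and the Liver biopsies section both promise a histological answer, the baseline biopsy is named as comparator, and no other before-after method is given. Following the plan as written yields a responder-only comparison, which is more than a missing detail.

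**Stronger readings that a reader might infer.** One is that the comparison is certain to overstate benefit. The documents do not support that: choosing the extension could select in either direction, and a conclusion confined to continuing responders would not carry this selection bias. Another is that false improvement is more likely than not. The same formula does reach 81%, but only with a 50% pass rate, r = 0.5 and 45 biopsies. That needs 45/0.5 = 90 patients entering, so every planned recruit would have to opt in with no losses, although the plan allows for drop-out from 30 to 25 per group.

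**Conclusion.** The concern holds as a matter of expected direction. Paired histology will come from opted-in patients who passed week 48, with no comparator, so a matched-pair test can be expected to overstate the long-term effect the précis says the trial will determine. On the assumptions shown, the shift runs from about 0.2 SD (75% pass rate, r = 0.5) to 0.03 SD (95%, r = 0.3), and it vanishes if the rule is unrelated to histology. The documents do not allow a narrower figure. The direction rests on a positive link between week-48 response and histological change, which the sponsor's pilot makes likely for histological response in general but not for fibrosis. The primary 24-week comparisons are unaffected. This is a cheap improvement to the analysis text and the claims.

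**What to change.** 1. In Statistical analyses, make the main histological summary the proportion improved from baseline to exit biopsy among all patients who start the extension. Pre-state the definition of improved on the NAFLD activity score, which the trial already collects.
2. Count week-48 futility withdrawals as not improved. Count other missing exit biopsies (drop-out, hemoglobin below 10 g/dL) as not improved in the main analysis, and leave them out in a sensitivity analysis.
3. Report fibrosis separately as improved, stable or worse, because a binary improvement measure cannot describe stability.
4. Keep the paired change in continuing responders, but label it descriptive and limited to them. Note that their doses are mixed, since some revert to their original dose after week 48.
5. In the précis and the Liver biopsies section, replace the wording about determining an effect and halting progression with descriptive wording.
6. Reconcile the précis, Extended Treatment Phase, Liver biopsies, Monitoring subjects, and Risks and Discomforts sections on who has the exit biopsy and when. They variously say all patients or those who continue, two to three biopsies or three, and 30 months, 120 further weeks or three years.

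This costs analysis wording only, with no added biopsies or visits. The downside is a lower, more conservative improvement rate, which may understate benefit because the week-48 rule is not a histological test, and a more modest claim.
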